2.2 Secondary Objective

- Evaluate patient satisfaction with aromatherapy at completion of study.
- Evaluate the antiemetic administration between **nausea/vomiting symptom** intervention and control groups during the 48-hour intervention time span.
- Evaluate the number and incidence of unit falls pre and post intervention.

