3.2 Secondary Outcome Measures

Patient Satisfaction with Aromatherapy

A brief semi-structured questionnaire will also be administered to evaluate patient satisfaction with the intervention at the 48-hour completion time.

Evaluate the antiemetic administration between **nausea/vomiting symptom intervention and control groups**

Data will also be collected from the electronic medical record related to antiemetic medications administered (dose, route, frequency) during the 48-hour intervention.

Evaluate the number and incidence of unit falls pre and post intervention

Fall rates will also be evaluated using the total number of falls reported to the National Database of Nurse Quality Indicators during the baseline and intervention timeframes. Demographic data will be collected including age, gender, and race/ethnicity.

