The study team initial visit will be at 0 hours (visit 1) and follow-up visits will be completed at 24 hours (visit 2) and 48 hours (visit 3). During visit 2 (Monday-Friday only), the study team will remind participating patients to complete their symptom journal, will answer any study-related questions, and will inquire about any aromatherapy side effects. During visit 3, a study team member will instruct the patient to complete the 48-hour symptom measures in the journal and will complete a brief intervention satisfaction questionnaire (Appendix C) with the patient (intervention group only). Patients will be provided a \$25 gift card to show appreciation for their time in the study. After symptom data collection is completed, a study team member will review and document antiemetic medication administration from the electronic medical record during the 48-hour intervention time frame. **Antiemetic administration will be captured on an Excel spreadsheet on a secure Microsoft Team for intervention and control participants in the nausea/vomiting symptom group. Included medications are scopolamine, lorazepam, promethazine, prochlorperazine, olanzapine, dexamethasone, Marinol, and ondansetron indicated for nausea/vomiting. Medication type, dose, order type (scheduled vs. PRN), and number of doses will be documented for antiemetics administered during the study timeframe.** Concomitant medications (e.g., antiemetic medications, steroids, benzodiazepines) will not be controlled as part of the study as the intent is not to alter standard practice for symptom treatment, but rather to provide an adjuvant to help reduce symptom burden. However, it is reasonable to expect that the need for PRN (available as needed) medications prescribed for nausea/vomiting or anxiety may be less in the treatment group compared to control during the 48 hours of inhaled aromatherapy. Because antiemetic and benzodiazepine medications may contribute to an increase in fall risk (Seppala et al., 2018; Wildes et al., 2018), we also plan to observe fall events during the study timeframe. Unit fall total numbers and incidence data will additionally be obtained from data reported to the National Database for Nurse Quality Indicators (NDNQI) for 12 months prior to implementation and 12 months during study implementation.

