9.0 Reportable Events

Inhaled essential oils including lavender, peppermint, and mandarin are generally considered safe if used as indicated. The essential oils used in this study are infused within an adhesive patch, so will not come in direct contact with the skin. However, if the essential oil patch is used not as indicated (e.g. oil applied directly to the skin, oil ingested), the risk of adverse event occurrence may increase.

Adverse Event: Defined as any problematic medical occurrence in a study participant who has received the intervention including inhaled lavender, peppermint, or mandarin essential oil, regardless of possibility of a causal relationship. Adverse events will be documented after the participant begins receiving the intervention.

The occurrence and nature of each participant's medical condition will be documented by study personnel prior to enrollment. Study personnel will document any changes in medical condition and/or the occurrence and description of any adverse event during the study. Events that occur from inhaled essential oil administration up to 72 hours after will be recorded (allows for 24 hours of monitoring after intervention ends). Events will be reviewed during data safety monitoring to determine causality.

Significant Adverse Event: Defined as a life-threatening condition (i.e. immediate risk of dying); severe/permanent disability; a significant hazard, contraindication, side effect, or precaution as deemed by the Data Safety Monitoring team to be caused by the intervention. Investigators will determine causality based on the participant's clinical course, medical history, and administered medications.

Adverse and Significant Adverse Events will be reported to the IRB within 5 business days from discovery if they are determined to be (1) unexpected; (2) related or possibly related to participation in the study; (3) finding suggests that the research procedures involve a greater harm risk than previously anticipated; (4) occurrence of unanticipated adverse device effects.

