12.0 Statistical Considerations

SAS and/or R statistical packages will be used to analyze primary outcomes, secondary outcomes, and demographic sample data.

Primary Outcomes

Comparisons between the intervention and control groups for differences in the CINVR and anxiety tools will be analyzed using mixed-model ANOVA, with time (baseline, 24 hours, 48 hours) repeated within subject. Chi-square tests will be used to compare the groups for differences in the proportions of patients prescribed medications for nausea/vomiting or anxiety. Separate analyses will be performed for the two symptom groups. A two-sided 5% significance level will be used for all tests.

Sample size justification: With sample sizes of 50 patients within each symptom group, 25 intervention/25 control within each symptom group, the study will have 80% power to detect an effect size of 0.81 between intervention and control within each symptom group, based on a two-sample t-test calculation and a two-sided 5% significance level. The recruitment target will be 112 participants (56 per symptom group) to account for a 10% drop out rate.

Secondary Outcomes

Descriptive statistics will be used to analyze frequencies and percentages of the patient satisfaction questionnaire responses, documented antiemetic administration, and number of unit falls. The number of (1) total antiemetic medication doses and (2) doses for each individual medication (i.e., Ativan, promethazine) will be compared between the control and intervention groups for the nausea/vomiting symptom group. The percentage change for number of falls will be calculated by comparing number of falls 12 months prior to intervention implementation to 12 months during implementation.

Descriptive statistics will be used to summarize the demographics of the study sample (frequencies and percentages for categorical variables, means and standard deviations for continuous variables).

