15.0 Follow-up and Record Retention

Study duration including data collection and analysis will take approximately eighteen months. Once data collection has been completed and data analyzed, completed assessments will be stored on a secure REDCap database. Once it has been determined that original data is no longer needed, data files will be secured with password protected computer, and all paperwork associated with the study will be discarded via a security container. Data, analysis, and consent forms will be secured for the required length of time required by the IRB and then will be destroyed appropriately.

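### Section 12 compares unit falls only as a percentage change in their number, which at a constant fall rate simply equals the change in patient-days, although incidence is part of the objective and its data will be obtained

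*Combined protocol and SAP*

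**What the plan says.** Four sections of the combined protocol and SAP deal with unit falls.

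- **Section 2.2 (objective):** "Evaluate the number and incidence of unit falls pre and post intervention". The outcome heading in Section 3.2 repeats this.
- **Section 3.2 (outcome definition):** "Fall rates will also be evaluated using the total number of falls reported to the National Database of Nurse Quality Indicators". The term is a rate, but the stated ingredient is a total, and no denominator is named.
- **Section 7.0 (data):** "Unit fall total numbers and incidence data will additionally be obtained from data reported to the National Database for Nurse Quality Indicators", for 12 months before and 12 months during implementation.
- **Section 12.0 (analysis):** falls appear twice. The list of items to be summarised descriptively ends with "documented antiemetic administration, and number of unit falls". The comparison then reads "The percentage change for number of falls will be calculated by comparing number of falls 12 months prior to intervention implementation", set against the 12 months during implementation.

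Both Section 12.0 statements use the number. No section says how the incidence data will be summarised or compared.

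**The concern.** A count of falls depends on how many patient-days the units delivered as well as on how often patients fall. The two periods have equal calendar length, but nothing makes them equal in occupancy. A percentage change in the raw count therefore mixes a change in fall rate with a change in census, and the reader cannot separate the two.

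Followed literally, Section 12.0 could report a busier year as an increase in falls, or report no change when the rate had moved. The incidence data that would avoid this are already to be obtained but have no stated analysis. If the measure is left open until the figures are in, the choice between count and rate could also depend on which looks better.

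**Working it through.** **Plan's own figure.** There is none to reproduce. The documents give no fall count, fall rate, patient-days or unit size. The check is therefore algebraic, with illustrative inputs.

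**Inputs from the documents.**
- Measure compared: number of falls (Section 12.0).
- Periods: 12 months before and 12 months during (Sections 7.0 and 12.0).
- Data to be obtained: totals and incidence (Section 7.0).

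**Assumed inputs.** Patient-day changes between -20% and +20%, and a rate change of 0% or -10%.

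**Formulas.**
- Expected falls = rate x patient-days.
- Change in count = (1 + rate change) x (1 + patient-day change) - 1.
- Rate ratio = 1 + rate change, because patient-days cancel.

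**Results.**

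| Rate change | Patient-day change | Calculation | Change in count (as planned) | Rate ratio |
|---|---|---|---|---|
| 0% | -20% | 1.00 x 0.80 - 1 | -20% | 1.00 |
| 0% | -10% | 1.00 x 0.90 - 1 | -10% | 1.00 |
| 0% | +10% | 1.00 x 1.10 - 1 | +10% | 1.00 |
| 0% | +20% | 1.00 x 1.20 - 1 | +20% | 1.00 |
| -10% | +10% | 0.90 x 1.10 - 1 | -1% | 0.90 |
| -10% | +11.1% (1/0.90 - 1) | 0.90 x 1/0.90 - 1 | 0% | 0.90 |
| -10% | +20% | 0.90 x 1.20 - 1 | +8% | 0.90 |

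At a constant rate the planned figure is the percentage change in patient-days. When the rate has fallen by 10%, an 11.1% rise in patient-days hides it completely, and a larger rise reverses its sign. The rate ratio is unaffected in every row.

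**The case against.** The strongest reply is that this is an omission and not a conflict. The objective, the Section 3.2 heading and the data plan all include incidence, Section 3.2 speaks of rates, and nothing in Section 12.0 says that incidence will not be reported. The outcome is descriptive, with no test attached, and no passage suggests that census will change.

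Most of that is right, and it limits the point. A reader might infer that the plan has abandoned incidence; the documents do not say so. What remains is that Section 12.0 does name one before/during comparison, and that comparison uses the count. The wording in Section 3.2 does not repair this, because it builds the rate from the total.

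Three other stronger readings are tempting and should not be drawn.

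- **The count always moves one-for-one with census.** This is exact only at a constant fall rate. With a rate 10% lower, a 10% rise in patient-days moves the figure from -10% to -1%, which is 9 points and not 10.
- **The sponsor will present a change in unit falls as an effect of aromatherapy.** Section 7.0 links falls to antiemetic and benzodiazepine use and expects that as-needed medication may be lower in the treatment group, so a reader might infer this. But no passage attributes a change in unit falls to the patches, and Section 12.0 is purely descriptive. A plain label on the comparison is enough.
- **Falls among control participants will go unrecorded.** Section 7.0 says "we also plan to observe fall events during the study timeframe" without giving a procedure, and Section 9.0 defines an adverse event as follows: "Defined as any problematic medical occurrence in a study participant who has received the intervention including inhaled lavender, peppermint, or mandarin essential oil". But Section 9.0 also has personnel document changes in medical condition, after referring to each participant's condition, and that is not confined to oil recipients. This is a separate matter, and the point here does not rest on it.

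**Conclusion.** The point holds as a limited one. The only falls comparison stated in Section 12.0 is confounded with census, and half of a stated secondary objective has planned data but no stated analysis. The equal 12-month periods do not remove the problem.

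The form of the distortion is certain, since it follows from expected falls being rate times patient-days. Its size in this trial is unknown, because the documents give no census figures; the percentages in the table are illustrations. The consequence is modest: the outcome is secondary, descriptive and outside the randomised comparison, and no primary conclusion depends on it. The change is worth considering because the better measure uses data already planned for collection.

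**What to change.** In Section 12.0, before the falls data are seen:

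- Keep the number of falls and its percentage change, since number is part of the objective.
- Add the fall incidence rate for each 12-month period, with the denominator stated (for example falls per 1,000 patient-days, if that is the measure the national database supplies; the documents do not define it).
- Make the before/during rate ratio with a 95% CI the main falls comparison.
- State whether results are given by unit or pooled. Section 4.1 names two possible units. If rates are pooled, use total falls divided by total patient-days and not a simple average of unit rates.
- Describe the result as a non-randomised, unit-level comparison.

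In Section 3.2, change the wording so that fall rates are evaluated from falls and their denominator, and not from the total alone.

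The cost is a few sentences. The one practical burden is that patient-day denominators may have to be requested with the incidence data, for pooling across units and for the CI. Where counts and rates are both supplied, patient-days can be recovered as falls divided by rate, but not for a period with no falls, and only approximately if rates are rounded.

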13.0 Data Management

Patient data collected from the electronic medical record will be documented in a secure electronic REDCap database. Paper signed informed consents and HIPAA authorizations will be stored in a file in a locked office. Demographic data, data from the symptom journal, and intervention satisfaction responses will be transferred from paper by a study team member into REDCap and paper documents will be stored in a secure, locked office. This study involves minimal risk for participants. All data will be stored via secure REDCap database, which is backed up automatically every day. Only study team members will have access to the data. All computers used for data storage and analysis will be password protected. Only aggregated data will be disseminated, and raw data will be destroyed after data analysis is complete.

14.0 Privacy/Confidentiality Issues

All data will be stored on a secure REDCap database. All computers used for data storage and analysis will be password protected and only trained study personnel will have access to data. A unique blinded identifier will be assigned to each participant record prior to analysis. The results of the study will be analyzed and reported as aggregate data and no participant or individual responses will be identified.

15.0 Follow-up and Record Retention

Study duration including data collection and analysis will take approximately eighteen months. Once data collection has been completed and data analyzed, completed assessments will be stored on a secure REDCap database. Once it has been determined that original data is no longer needed, data files will be secured with password protected computer, and all paperwork associated with the study will be discarded via a security container. Data, analysis, and consent forms will be secured for the required length of time required by the IRB and then will be destroyed appropriately.

17.0 Appendix

Appendix A: Demographic Questionnaire

1. What is your age in years? (or prefer not to say)
2. What gender do you identify with?
 - a. Woman
 - b. Man
 - c. Transwoman
 - d. Transman
 - e. Genderqueer
 - f. not listed
 - g. prefer not to say
3. What race do you most closely identify with?
 - a. White/Non-Hispanic
 - b. Latino
 - c. Black or African American
 - d. Native American or American Indian
 - e. Asian or Pacific Islander
 - f. Other
 - g. Prefer not to say

Appendix B: Sample of Journal

Page 1

	 
My Aromatherapy Journal
 
Patient's Name:
 <hr data-bbox="941 1470 1396 1480"/>
--	---

Page 2

Today's Date: _____ Time Patch Administered: _____ Essential Oil Administered: _____
	
My goals for today are: _____ _____ _____

Measurement Tool Goes Here
 

	
Write, draw or doodle something you are grateful for: _____ _____ _____ _____ _____

Appendix C: Aromatherapy Experience/Satisfaction Questionnaire

1. Tell me about your experience with aromatherapy in the hospital.
2. What was your satisfaction with aromatherapy on a scale of 1-10 (10 being extremely satisfied)?
3. How likely are you to use aromatherapy again in the hospital on a scale of 1-10 (10 being extremely likely)?
